ACQ-6 = asthma control questionnaire-6; AE = adverse event; anti-HBc = hepatitis B core antibody; anti-HBs = hepatitis B surface antibody; BD = bronchodilator; CRS = chronic rhinosinusitis; ECG = electrocardiogram; EDN = eosinophil derived neurotoxin; FeNO = fractional exhaled nitric oxide; FSH = follicle-stimulating hormone; HbA1c = haemoglobin A1c; HBsAg = hepatitis B surface antigen; HIV = human immunodeficiency virus; HRT = hormone replacement therapy; ICF = informed consent form; IgE = immunoglobulin E; IGRA = interferon gamma release assay; NT-proBNP = N-terminal prohormone of B-type natriuretic peptide; SAE = serious adverse event; SARS-CoV-2 = severe acute respiratory syndrome coronavirus 2; SGRQ = St George’s respiratory questionnaire; SID = subject identification; SNOT-22 = sino-nasal outcome test-22; CCI SOC = standard of care; SV = study visit; TB = tuberculosis; VAS = visual analogue scale.

Table 2 Schedule of Activities: Study Intervention and Follow-up Periods

Period	Study Intervention							Follow-up		
Visit Number	SV4 (Randomisation)	SV5 (TC)	SV6	SV7	SV8	SV9	SV10	SV11	SV12	E/D
Study Day	1	2	8 (± 3)	29 (± 3)	57 (± 3)	85 (± 3)	113 (± 3)	141 (± 3)	169 (± 3)	
Study Week	0	0	1	4	8	12	16	20	24	
Efficacy assessments										
ACQ-6	X		X	X	X	X	X		X	X
SGRQ	X			X		X	X		X	X
SNOT-22 (comorbid CRS participants only)	X		X	X	X	X	X			
At-home eDiary completion and spirometry use	Twice daily throughout the intervention period.									
Assess adherence to at-home eDiary completion, spirometry, and SOC medication use	X	X	X	X	X	X	X	X	X	
Assessment of asthma exacerbations	X	X	X	X	X	X	X	X	X	X
PGI-BR							X			
Study participant feedback questionnaire (optional)	X						X		X	X
FeNO	X		X	X	X	X	X	X	X	X
Airwave oscillometry (pre-administration of study intervention)	X		X	X	X	X	X			
Airwave oscillometry (4 hours post-administration of study intervention)	X ^a									

Table 2 Schedule of Activities: Study Intervention and Follow-up Periods

Period	Study Intervention							Follow-up		
Visit Number	SV4 (Randomisation)	SV5 (TC)	SV6	SV7	SV8	SV9	SV10	SV11	SV12	E/D
Study Day	1	2	8 (± 3)	29 (± 3)	57 (± 3)	85 (± 3)	113 (± 3)	141 (± 3)	169 (± 3)	
Study Week	0	0	1	4	8	12	16	20	24	
In-clinic spirometry (pre-BD) (pre-administration of study intervention)	X		X	X	X	X	X	X	X	X
In-clinic spirometry (4 hours post-administration of study intervention)	X ^a									
In-clinic spirometry (post-BD)	X				X		X			
Safety assessments										
Concomitant medications	X	X	X	X	X	X	X	X	X	X

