Physical examination	X ^b		X ^b	X ^c	X ^c					
Weight	X						X		X	X
Vital signs	X		X	X	X	X	X	X	X	X
ECG	X ^d						X		X	X
Echocardiogram ^e						X ^f				
Assessment of AEs/SAEs	X	X	X	X	X	X	X	X	X	X
Injection site reactions	X		X	X	X	X	X			X
SARS-CoV-2 PCR test ^g	X		X	X	X	X	X	X	X	X
Collect blood^h for:										
Haematology	X		X	X	X	X	X		X	X
Coagulation parameters	X		X	X	X	X	X		X	X
Serum chemistry	X		X	X	X	X	X		X	X

Table 2 Schedule of Activities: Study Intervention and Follow-up Periods

Period	Study Intervention							Follow-up		
Visit Number	SV4 (Randomisation)	SV5 (TC)	SV6	SV7	SV8	SV9	SV10	SV11	SV12	E/D
Study Day	1	2	8 (± 3)	29 (± 3)	57 (± 3)	85 (± 3)	113 (± 3)	141 (± 3)	169 (± 3)	
Study Week	0	0	1	4	8	12	16	20	24	
NT-proBNP ^e					X	X	X		X	X
PK (serum)	X		X	X	X	X	X	X	X	X
Immunogenicity (serum)	X		X	X	X	X	X		X	X
Exploratory biomarkers (serum)	X		X	X	X	X	X	X	X	X
SARS-CoV-2 serology test (serum)	X						X			X
Total IgE (serum)	X						X		X	
Allergen-specific IgE (serum)	X									
EDN (plasma)	X			X			X		X	
sST2 (serum)	X						X			
RNA PAXgene	X						X			
CCI [REDACTED]	CI									
CCI [REDACTED]	CI									
DNA for exploratory genetics evaluation (optional)	X ⁱ									
Collect urine for:										
Urinalysis	X		X	X	X	X	X			X
Pregnancy test ^j	X			X	X	X	X		X	X

Table 2 Schedule of Activities: Study Intervention and Follow-up Periods

Period	Study Intervention							Follow-up		
Visit Number	SV4 (Randomisation)	SV5 (TC)	SV6	SV7	SV8	SV9	SV10	SV11	SV12	E/D
Study Day	1	2	8 (± 3)	29 (± 3)	57 (± 3)	85 (± 3)	113 (± 3)	141 (± 3)	169 (± 3)	
Study Week	0	0	1	4	8	12	16	20	24	
Collect nasal sample for:										
Nasal mucosal sampling (lining fluid)	X			X	X	X	X	X	X	
Nasal mucosal sampling (mRNA) ^k	X						X			
Verify eligibility criteria	X									
Randomisation	X									
Study intervention administration^l	C			C	C	C				
Pandemic impact assessment^m	X	X	X	X	X	X	X	X	X	X
Exploratory cough sub-study only										
At-home cough monitoring (for the 24 hours post-clinic visit)							X			
Cough VAS							X			

^a Airway oscillometry and spirometry performed 4 hours (± 15 minutes) post administration of study intervention will require 4 hours withhold of bronchodilator (see Section 6.5.3).

^b Brief physical examination.

^c Complete physical examination.

^d Triplicate ECG. The mean value of each parameter from the triplicate will be used as the baseline value.

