It is recognised that depending on the location and facilities of a clinical site, study visit attendance may place participants at risk of exposure to SARS-CoV-2. Furthermore, it is recognised that more general population-level measures to reduce infection rates (eg, travel restrictions) may inhibit the ability of participants to attend study visits. Necessary healthcare responses at sites to the pandemic (eg, additional infection control measures) may also inhibit the ability of a clinical site to effectively and properly conduct the study. Study visit attendance for dosing and for clinical assessments of treatment response are critical for the scientific value of the study.

Therefore, investigators should not enrol participants unless they have reasonable confidence that throughout the duration of the study:

- Participants will be able to attend study visits, whilst avoiding contact with concentrations of COVID-19 patients (eg, hospital entrances used by such patients); and
- The site will be able to conduct the study effectively and safely, considering relevant national and local factors.

The primary endpoint will be analysed using a repeated measures mixed effect model which, in the event of missing data, uses all data that are available. The sponsor will monitor the number of discontinuations, withdrawals, missed visits and other missing data.

AstraZeneca will routinely conduct risk-based enrolment assessments on a country and site level during the pandemic phase of COVID-19, and study monitoring will focus, in part, on AEs associated with new onset SARS-CoV-2 infection and participants withdrawn due to COVID-19 illness.

All site staff should wear personal protective equipment in accordance with local or national guidelines.

If, for reasons related to the COVID-19 pandemic, a participant is not able to attend their scheduled visit within the ± 3 day visit window, they can have their visit rescheduled within 14 days of the original scheduled visit; however, visits that cannot be rescheduled within a 14 day window must be skipped and participants should continue at the next scheduled visit.

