3.1.2 Study day

Whenever data are summarised over time, study day will be calculated based on the actual assessment date in relation to date of first IP administration.

If actual assessment date is prior to first IP administration, then study day will be:

$$\text{Study day} = \text{Actual assessment date} - \text{first IP administration date.}$$

If actual assessment date is on or after first IP administration, then study day will be:

$$\text{Study day} = \text{Actual assessment date} - \text{first IP administration date} + 1.$$

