3.1.4 Analysis visit and study phase windows

For the exacerbation and CompEx related analyses no analysis visit windows will be applied.

For PK related analyses no analysis visit windows will be applied and the actual visits and timepoints will be used instead.

Visit windows will be used for all assessments to allow for by-visit analyses, since not all assessments might be performed on the scheduled day. Unless specified otherwise, the efficacy and safety analyses will be based on the analysis visit windows. The actual assessment day will be mapped to the planned study visit following the analysis visit windowing rules below:

- If more than one assessment falls within a visit window, the closest non-missing assessment to the scheduled day will be used in the analysis.
- If more than one non-missing assessment actual dates are equidistant from the target day, the earlier assessment will be used in the analysis.
- If more than one assessment is selected (i.e. due to teste repetitions) the average for numerical values / worst case for categorical values will be used in the analysis

The visit windows for the visits following baseline are constructed in such a way that the upper limit of the interval falls half way between the two visits, rounded up to the nearest integer. The lower limit of each window will be the mean of the two adjacent planned study days +1, rounded up to the nearest integer, except for the first post-treatment visit.

Table 3 Analysis visit windows for in-clinic spirometry, FeNO, vital signs, SARS-Cov-2 PCR test, exploratory biomarkers (serum)

Protocol Visit	Week	Analysis Visit	Scheduled Study Day	Visit Window for Analysis (Days)
SV4	Week 0	Baseline	1	All assessments prior to the first administration of investigational product
SV6	Week 1	Week 1	8	All assessments on or after the first administration of investigational product to Day 19
SV7	Week 4	Week 4	29	20 to 43
SV8	Week 8	Week 8	57	44 to 71
SV9	Week 12	Week 12	85	72 to 99
SV10	Week 16	Week 16	113	100 to 127
SV11	Week 20	Week 20	141	128 to 155
SV12	Week 24	Week 24	169	≥ 156

SV = Study Visit.

For vital signs, if the selected day is a dosing day, timepoints as per SOA within the day need to be considered (ie, Baseline, Day1: post-dose, Day1: 30m, Day1: 60m, Day1: 120m, Week1, etc...).

For in-clinic spirometry pre-BD at day 1 timepoint at 4 hour post dose need also to be considered.

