Table 4 Analysis visit windows for ACQ-6, haematology, coagulation parameters, serum chemistry and immunogenicity

Protocol Visit	Week	Analysis Visit	Scheduled Study Day	Visit Window for Analysis (Days)
SV4	Week 0	Baseline	1	All assessments prior to the first administration of investigational product
SV6	Week 1	Week 1	8	All assessments on or after the first administration of investigational product to Day 19
SV7	Week 4	Week 4	29	20 to 43
SV8	Week 8	Week 8	57	44 to 71
SV9	Week 12	Week 12	85	72 to 99
SV10	Week 16	Week 16	113	100 to 141
SV12	Week 24	Week 24	169	≥142

SV = Study Visit.

Table 5 Analysis visit windows for SNOT-22, Airwave Oscillometry and urinalysis

Protocol Visit	Week	Analysis Visit	Scheduled Study Day	Visit Window for Analysis (Days)
SV4	Week 0	Baseline	1	All assessments prior to the first administration of investigational product
SV6	Week 1	Week 1	8	All assessments on or after the first administration of investigational product to Day 19
SV7	Week 4	Week 4	29	20 to 43
SV8	Week 8	Week 8	57	44 to 71
SV9	Week 12	Week 12	85	72 to 99
SV10	Week 16	Week 16	113	≥100

SV = Study Visit.

Table 6 Analysis visit windows for SGRQ

Protocol Visit	Week	Analysis Visit	Scheduled Study Day	Visit Window for Analysis (Days)
SV4	Week 0	Baseline	1	All assessments prior to the first administration of investigational product
SV7	Week 4	Week 4	29	All assessments on or after the first administration of investigational product to Day 57
SV9	Week 12	Week 12	85	58 to 99
SV10	Week 16	Week 16	113	100 to 141
SV12	Week 24	Week 24	169	≥142

SV = Study Visit.

Table 7 Analysis visit windows for NT-proBNP assessment

Protocol Visit	Week	Analysis Visit	Scheduled Study Day	Visit Window for Analysis (Days)
SV4	Week 0	Baseline		All assessments prior to the first administration of investigational product
SV8	Week 8	Week 8	57	All assessments on or after the first administration of investigational product to Day 71
SV9	Week 12	Week 12	85	72 to 99
SV10	Week 16	Week 16	113	100 to 141
SV12	Week 24	Week 24	169	≥142

SV = Study Visit.

Table 8 Analysis visit windows for ECGs and total IgE (serum)

Protocol Visit	Week	Analysis Visit	Scheduled Study Day	Visit Window for Analysis (Days)
SV4	Week 0	Baseline	1	All assessments prior to the first administration of investigational product
SV10	Week 16	Week 16	113	All assessments on or after the first administration of investigational product to Day 141
SV12	Week 24	Week 24	169	≥142

SV = Study Visit.

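### The SAP's Week 1 window for airwave oscillometry also captures the 4-hour post-dose reading on Day 1, which becomes the Week 1 value when SV6 is missed or late

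*Protocol*

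**What the plan says.** **The reading.** Protocol Section 1.3, Table 2, lists AO at SV4 before dosing and again afterwards: "Airwave oscillometry (4 hours post-administration of study intervention"). Footnote a fixes the time for AO and "spirometry performed 4 hours (± 15 minutes) post administration of study intervention". The pre-dose reading is the baseline under SAP Section 3.1.1.

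**The window.** SAP Section 3.1.4, Table 5 ("Analysis visit windows for SNOT-22, Airwave Oscillometry and urinalysis"), gives Week 1 a scheduled day of 8 and this content: "All assessments on or after the first administration of investigational product to Day 19".

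**The selection rule.** Where a window holds several readings, "the closest non-missing assessment to the scheduled day will be used in the analysis". If two are equally distant, the earlier is used.

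**The exceptions.** Under Table 3, the SAP tells the programmer to keep within-day timepoints apart for vital signs and adds: "For in-clinic spirometry pre-BD at day 1 timepoint at 4 hour post dose need also to be considered". Table 3 does not cover AO. Nothing equivalent appears under Table 5, in Section 3.6.1 (derivation of AO variables) or in Section 4.2.6.1 (analysis of AO).

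**The endpoint.** Protocol Table 4 lists change from baseline in AO parameters at Weeks 1, 4, 8, 12 and 16. It gives the 4-hour spirometry its own acute endpoint but has none for the 4-hour AO.

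**The concern.** Followed literally, the SAP gives the 4-hour AO reading one role in the by-visit analysis: candidate for Week 1. It then enters the Week 1 summaries and the MMRM for R5, R20, R5-R20 and AX as if it were a one-week response.

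The two readings differ in more than time since dose. Post-bronchodilator spirometry is scheduled at SV4, and Section 1.3 puts assessments on dosing days before the dose unless stated otherwise, so a bronchodilator has been given earlier that day. Protocol Section 6.5.3 asks for at least 6 hours without a short-acting bronchodilator before scheduled AO, whereas footnote a of Table 2 asks for 4 hours before the post-dose reading.

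Two things can go wrong. A Week 1 value that should be missing, which the MMRM is meant to handle, is filled with a same-day value. A genuine SV6 reading can also be set aside in favour of that value.

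**Working it through.** **Inputs**
- Day 1 is the day of first dosing: "study day will be calculated based on the actual assessment date in relation to date of first IP administration", plus one on or after that date (SAP Section 3.1.2).
- SV6 is scheduled for Day 8 ± 3, so Days 5 to 11; SV7 is scheduled for Day 29 (Protocol Table 2).
- Late visits: for pandemic reasons participants may miss the ± 3 day window and "they can have their visit rescheduled within 14 days of the original scheduled visit" (Protocol Section 2.3.1.2). That reaches Day 8 + 14 = Day 22. A visit that cannot be held by then is skipped.
- Telemedicine visits are allowed in the same section; AO is not among the data they are said to collect.

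**Step 1: reproduce the SAP's window.** The upper limit is the midpoint of adjacent visits, rounded up: (8 + 29)/2 = 18.5, which gives Day 19. The next window starts at 18.5 + 1 = 19.5, which gives Day 20. Both match Table 5, and the later limits (43/44, 71/72, 99/100) reproduce in the same way.

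**Step 2: apply the selection rule.** Distance = |study day − 8|. For the Day 1 reading this is |1 − 8| = 7. The candidates are that reading and the SV6 reading, if SV6 falls on or before Day 19.

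| SV6 AO | Distance from Day 8 | Reading used as Week 1 |
|---|---|---|
| Days 5 to 11 (normal window) | 0 to 3 | SV6 |
| Days 12 to 14 | 4 to 6 | SV6 |
| Day 15 | 7 (tie, earlier wins) | Day 1, 4 hours |
| Days 16 to 19 | 8 to 11 | Day 1, 4 hours |
| Days 20 to 22 | in the Week 4 window | Day 1, 4 hours |
| Not done | none | Day 1, 4 hours |

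On Days 15 to 19 the SV6 reading is in the window and loses. On Days 20 to 22 it has left the window, so the Day 1 reading stands alone. The table assumes no unscheduled AO reading: the SAP also windows unscheduled visits, and one on Days 2 to 14 would be chosen ahead of Day 1.

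**Step 3: size.** The documents give no rate of missed or late SV6 visits. Assume 5% to 10%. With about 76 randomised per arm, 0.05 × 76 = 3.8 and 0.10 × 76 = 7.6, so about 4 to 8 per arm. If treatment has had no effect by 4 hours and the affected fraction is the same in each arm, a simple Week 1 contrast shrinks to between 1 − 0.05 = 0.95 and 1 − 0.10 = 0.90 of its true value.

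**The case against.** The strongest reply is that this hardly matters. AO is exploratory, Week 1 is one of five post-baseline AO visits, and no test in the hierarchy uses it. An SV6 visit held on time always wins. Losing a real SV6 reading requires a visit on Days 15 to 19, which the protocol provides for only through the pandemic rescheduling rule. All of that is right, and it limits the importance of the point.

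The 5% to 10% has no source in the documents. The plan's only 5% allowance is for participants ineligible for the primary analysis, which is a different quantity. The base of 76 is also an upper bound, because AO from SV6 onwards is done only if the baseline AO succeeded (Protocol Section 8.1.3). The per-arm count is therefore illustrative.

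The bronchodilator difference should not be overstated. Footnote a requires a 4-hour withhold for this reading, and Section 6.5.3 has short-acting bronchodilators withheld after the post-bronchodilator spirometry. Any residual effect is uncertain; what is certain is that the washout conditions differ from those at SV6.

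Nothing is wrong with the protocol's schedule row. The gap is in the SAP. None of this removes the mechanism: the SAP's rules lead to the 4-hour reading, and no sentence in it excludes that reading.

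**Conclusion.** The concern holds. Applied as written, SAP Section 3.1.4 and Table 5 report the Day 1 4-hour AO reading as Week 1 when SV6 AO is missing or falls on Days 15 to 19, and also on Days 20 to 22, barring an unscheduled reading nearer Day 8. This is a stated rule giving a wrong value, since the SAP already recognises the same problem for spirometry and vital signs. The day ranges follow from the documents alone. The figure of 4 to 8 per arm rests on the assumed 5% to 10%, and the matching dilution rests further on no effect by 4 hours. The primary and secondary endpoints are untouched; this is a minor correction.

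**What to change.** Give AO its own row or footnote in SAP Table 5, with the Week 1 window running from Day 2 to Day 19. SNOT-22 and urinalysis share the table and can stay as they are. Extend the sentence on the 4-hour spirometry timepoint to AO, so that the Day 1 post-dose reading is held as a separate timepoint and excluded from every by-visit summary and the MMRM. A descriptive summary by arm at that timepoint would give the reading a stated use. When no AO is obtained on Days 2 to 19, Week 1 is then missing and the MMRM handles it.

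The cost is one row, one sentence and a small programming change. No new data are needed and trial conduct does not change.

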2 INTRODUCTION

MEDI3506 is a human IgG1 mAb that binds to human IL-33. MEDI3506 binds full length and mature forms of human IL-33 with exceptionally high affinity and prevents IL-33 binding to soluble (sST2) and membrane-bound forms of ST2 (also known as IL-1RL1) receptor. Several clinical and non-clinical studies point to the IL-33/ST2 signalling axis playing a key role in the pathogenesis of asthma. Thus, blocking this signalling pathway could be of therapeutic benefit in asthma. MEDI3506 is currently in development for the treatment of asthma, AD, COPD, and DKD.

2.1 Study Rationale

The MEDI3506 pre-clinical profile suggests that MEDI3506 can reduce asthmatic airway inflammation, improve epithelial integrity, reduce mucus production, and improve muco-ciliary transport. As such, MEDI3506 is hypothesised to impact on asthma disease status by increasing FEV₁ (and other physiological measures of lung function) and reducing frequency and severity of asthma exacerbations, thereby improving quality of life.

One Phase I clinical study of MEDI3506 (Study D9180C00001) was completed in December 2019. Study D9180C00001 was a first in human, randomized, placebo controlled, blinded (investigator and participant blinded; sponsor unblinded) clinical study in 88 participants to evaluate the safety, tolerability, PK, and immunogenicity of single and repeated doses of MEDI3506. MEDI3506 was generally found to be safe and well tolerated. For further details, refer to the IB.

This Phase II study aims to assess the efficacy and safety of MEDI3506 in adult participants with uncontrolled moderate-to-severe asthma.

2.2 Background

Asthma is a chronic inflammatory disease of the airways characterised by bronchial hyperreactivity and reversible airflow limitation. International treatment guidelines for asthma recommend ICS as first line therapy ([GINA 2020](#)). For individuals who are symptomatic on medium dose ICS monotherapy, step-up therapy with LABA is the recommended next treatment option followed by other controller therapies including leukotriene receptor antagonists, theophylline, and oral corticosteroids. ‘Biologic agents’ (eg, omalizumab and benralizumab) that inhibit specific molecular targets such as IgE or Th2 cytokines and their respective receptors are reserved for those with severe uncontrolled asthma. Furthermore, all currently approved asthma controller therapies have little or no impact on the natural history of the disease (ie, most people with moderate-severe asthma need life-long therapy). There is a clear unmet need for asthma therapies that not only better control symptoms, but lead to disease modification.

Numerous studies have shown a key role for IL-33 in asthma. The genes encoding IL-33 and ST2/IL1RL1 have been identified as major susceptibility loci for human asthma in several genome wide association studies (Bonnelykke et al 2014; Gudbjartsson et al 2009; Hirota et al 2011; Moffat et al 2010; Shrine et al 2019; Torgerson et al 2011; Wan et al 2012) and were among the few genes reproducibly found to be associated with asthma across diverse ethnic groups. In addition, a rare IL-33 loss-of-function mutation has been recently described that reduces blood eosinophil counts and protects from asthma (Smith et al 2017). The protective effect remained, although weaker, after correcting for eosinophil counts, suggesting that IL-33 may influence asthma risk in part by controlling blood eosinophil count, and also through additional biological pathways (Mousas et al 2017).

Two Phase II studies support a role for anti-IL-33 therapy in asthma treatment. In a proof-of-concept study involving adult patients with moderate-to-severe asthma, REGN3500 monotherapy (ICS and LABA maintenance therapy were withdrawn during the trial) met the primary endpoint of improvement in loss of asthma control and significantly improved lung function compared to placebo, meeting a key secondary endpoint (NCT03387852). In a separate Phase II clinical study, a single IV dose of etokimab was administered to patients with uncontrolled moderate-to-severe asthma despite being on treatment with high dose combination ICS plus LABA therapy. Compared with a placebo group, asthmatics treated with etokimab had a significant improvement in lung function (FEV₁) and a reduction in blood eosinophils (NCT03469934).

A detailed description of the chemistry, pharmacology, mechanism of action, and safety of MEDI3506 is provided in the IB.

